Brief Title: Tonsil Surgery in Recurrent or Chronic Tonsillitis

ClinicalTrials.gov NCT04657549

Date: 2nd May 2023

Correction of sample size calculation

The estimated sample size that we first reported on the ClinicalTrials.gov register was 285 patients. This figure turned out to be wrong due to a calculation error. We have now corrected this calculation error. We emphasize that we have not altered the key parameters of the sample size calculation that must be determined and registered before the trial begins. Our parameters of alfa error=0.05, beta error=0.1, standard deviation=standard deviation and noninferiority limit=10 on the Tonsillectomy Outcome Inventory Scale (TOI-14), that we found in our prior article [Laajala et al. doi: 10.1007/s00405-020-05832-z] to be the minimum change a patient could sense, have all been determined at the planning phase of our trial. In this correction we do not change these parameters. What we do here is to correct the calculation error that we made when the data on the linear scale was log-transformed because of the nonnormality. The previously published wrong sample size calculations were based on a wrong standard deviation and on a wrong noninferiority limit on the log-scale resulting in a substantial error in the number of patients needed in each group. The correct sample size calculation is presented in the following paragraph.

Sample size

Our principal outcome is a disease-specific QoL questionnaire TOI-14 score measured at baseline and at 6 months of follow-up. According to Laajala et al. [doi: 10.1007/s00405-020-05832-z], a difference of 10 points is clinically significant. Further, the TOI-14 score was detected to be highly skewed to the right with excess zeroes at 6 months of follow-up, so we used a natural logarithmic transformation ($\log (1+TOI-14)$) in sample size calculations. Our hypotheses were (A) both surgically treated groups (TE+TT combined) are superior (mean 1.6 vs 3.0, SD=1.0) compared to the follow-up (WW), and (B) TT is noninferior to TE (change score mean 3.1, SD=0.7 with non-inferiority limit=0.4). In both calculations $\alpha=0.05$ and $\beta=0.10$ (power=0.90). According to this and taking into consideration the allocation ratio, (A) 7 and 28 patients in the WW and the combined TE+TT groups, respectively, and (B) 53 patients in the TE and the TT groups will be needed. Considering the allocation ratio WW:TE:TT = 1:2:2 and ensuring adequate sample size for each group, we decided to recruit 27 patients into the WW group and 53 in both the TE and the TT groups. Further assuming a drop-out rate of 10%, the sample size

for both surgically treated groups is 59 and for the follow-up group 30 patients (altogether 148). Sample size estimation was performed only for the principal outcome, and other comparisons are hypothesis generating only.”

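### Does hypothesis A claim that each operation beats WW when only the pooled surgical group is tested?

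*SAP*

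**What the plan says.** The Sample size section of the SAP sets two hypotheses on log(1+TOI-14). The first is "A) both surgically treated groups (TE+TT combined) are superior (mean 1.6 vs 3.0, SD=1.0) compared to the follow-up (WW". The second is "B) TT is noninferior to TE (change score mean 3.1, SD=0.7 with non-inferiority limit=0.4".

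The first calculation asks for "A) 7 and 28 patients in the WW and the combined TE+TT groups, respectively". For the non-inferiority question the stated requirement is 53 per surgical arm. With 1:2:2 allocation, the sponsor settles on more than A needs: "we decided to recruit 27 patients into the WW group and 53 in both the TE and the TT groups". Ten per cent drop-out raises this to 30, 59 and 59.

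The section ends: "Sample size estimation was performed only for the principal outcome, and other comparisons are hypothesis generating only". No separate TE v WW or TT v WW test is described, and A is not made conditional on B.

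**The concern.** To say that both groups are superior is, in ordinary usage, to say something about each of them. A pooled mean cannot support that: it shows that surgery on average differs from WW, and one effective arm can carry one that does nothing. If the closing sentence makes every other comparison exploratory, no confirmatory test of TT against WW or of TE against WW is left.

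At stake would be a conclusion that both operations work when only one does. B does not fully replace the missing comparison, because an inconclusive B leaves TT shown neither non-inferior to TE nor better than WW.

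**Working it through.** **Inputs (SAP, Sample size).** A: means 1.6 and 3.0, so a difference of 1.4; SD 1.0; WW to pooled surgery 1:4. B: SD 0.7, margin 0.4. α = 0.05, power 0.90. Evaluable numbers 27, 53 and 53. Neither sidedness nor the test is stated; I take the sidedness that reproduces each stated n.

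**The plan's own figures.**
- A, two-sided 0.05: n(WW) = (1 + 1/4) × [(1.960 + 1.282)/1.4]² = 6.70, so 7 and 4 × 7 = 28. Reproduced (one-sided 0.05 would give 6 and 24).
- B, one-sided 0.05: n = 2 × (1.645 + 1.282)² × 0.49/0.16 ≈ 52.5, so 53 per arm. Reproduced (one-sided 0.025 would give 65).
- Drop-out: 53/0.9 = 58.9, so 59; 27/0.9 = 30; 59 + 59 + 30 = 148. Reproduced.

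**What A is.** Three features of the text agree: the parenthesis directly after the word *both* says the groups are combined; one surgical mean (1.6) is given, not one per arm; and the sample size sets 7 WW patients against 28 in the combined group. Hypothesis, effect and n all describe one pooled contrast.

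**The troubling scenario.** Let WW = 3.0, TE = 1.6, TT = 3.0, with SD 1.0 within each arm. The surgical mean is (1.6 + 3.0)/2 = 2.3, a difference of 0.7 from WW. With SD 1.0, SE = √(1/27 + 1/106) = 0.2156, and power = Φ(0.7/0.2156 − 1.96) = Φ(1.29) = 0.90. Simulation (200,000 trials) gives:

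| Test of pooled surgery v WW, two-sided 0.05 | Significant |
|---|---|
| Student t | 82% |
| Welch t | 87% |
| Three-arm contrast | 90% |

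The t tests fall below 90% because two arm means 1.4 apart raise the pooled surgical SD to √(1 + 0.7²) = 1.22. These are not false positives for the pooled hypothesis: the true average difference is 0.7, not zero.

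**The same scenario under B.** If the arms share a baseline, so that 1.4 carries over to the change score, SE = 0.7 × √(2/53) = 0.136. The chance that B is met is Φ((0.4 − 1.4)/0.136 − 1.645) = Φ(−9.0), effectively zero.

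**The alternative.** Requiring both pairwise tests against WW, each at two-sided 0.05, would allow the claim for each operation in about 2.5% of trials in this scenario. Power when both arms share the same true effect (100,000 trials, 27/53/53):

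| True effect in both arms | Pooled (Student) | Both pairwise |
|---|---|---|
| 1.4 | >99.9% | >99.9% |
| 1.0 | >99% | 98% |
| 0.7 | 90% | 75% |
| 0.6 | 79% | 59% |

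**The case for a change.** The best case for acting has three parts.

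First, the same section elsewhere uses *both* to mean each arm, as in "we decided to recruit 27 patients into the WW group and 53 in both the TE and the TT groups", so a reader may carry that sense into A. This stands as a remark on wording. It does not outweigh the parenthesis that defines the term where it is used.

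Second, B protects in one direction only. If TT had its full effect and TE none, A would be significant equally often and B would be met in essentially every trial, although TE does nothing. That is correct arithmetic. But the two statements then made, that surgery on average beats WW and that TT is not inferior to TE, would both be true. Only the further step to TE alone would be wrong, and no rule in the SAP takes it.

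Third, B can be inconclusive when TT works: in 10% of trials if TT equals TE, and in 57% if TT is 0.2 worse, inside the margin. TT v WW at an effect of 1.2 would then have over 99% power: SE = √(1/27 + 1/53) = 0.236, and Φ(1.2/0.236 − 1.96) exceeds 0.99. This again moves a deficit from B's change score to A's scale. The 10% and 57% are B's type II error and show no fault in A.

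Gated pairwise tests would indeed need no extra patients and would leave the pooled test's power untouched. That makes them a reasonable option, but not a correction. It is also not certain that the closing sentence excludes them: it opens with the principal outcome, so the other comparisons it mentions may be those on other outcomes.

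**Conclusion.** No change to the plan is needed. Followed as written, A tests pooled surgery against WW, and the effect, SD and sample size given for it belong to that question. No stated number, power or threshold is wrong.

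The 82% to 90% is right under its assumptions: two-sided 0.05, SD 1.0 within each arm, 27/53/53 evaluable, and one operation wholly ineffective. It becomes an error rate only if *both* is read as *each*, against its own parenthesis, and a significant pooled test is then reported as a result for each operation. The SAP states no such reporting rule. With TT ineffective, B's failure would show it.

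The loose word is a clerical matter: dropping it would leave every calculation and test as it is. A pooled surgery question plus a TT v TE non-inferiority question is a coherent design, and whether to add confirmatory comparisons of each operation with WW is the sponsor's choice.

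### Hypothesis B's change score, SD and limit do not fit the one log scale the SAP prints, so 53 per group is not shown to give 90% power for a 10-point limit

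*SAP*

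**What the plan says.** The SAP was issued to correct a sample size. Its section on the correction says the earlier figures were "based on a wrong standard deviation and on a wrong noninferiority limit on the log-scale", and that the planning parameters are unchanged, among them a "noninferiority limit=10 on the Tonsillectomy Outcome Inventory Scale (TOI-14" scale.

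The Sample size section repeats that "a difference of 10 points is clinically significant". It describes the score as "highly skewed to the right with excess zeroes at 6 months of follow-up", "so we used a natural logarithmic transformation", and prints that transformation as log(1+TOI-14). No other scale is named.

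Under hypothesis A the combined surgical groups "are superior (mean 1.6 vs 3.0, SD=1.0) compared to the follow-up (WW"). The second hypothesis reads "B) TT is noninferior to TE (change score mean 3.1, SD=0.7 with non-inferiority limit=0.4"). The section does not say whether the change score is a difference of two logs or the log of a change in points. It gives no baseline mean and no maximum score, and it does not show how 10 points became 0.4.

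**The concern.** On the printed scale a change score is a difference of two logs. A mean change of 3.1 ending at 1.6 would need a very high starting level, and the watchful-waiting (WW) arm would then have to improve greatly without surgery. The limit raises a second question. A fixed number of points corresponds to different log distances at different score levels, and 0.4 does not correspond to 10 points at the level hypothesis A gives for the surgical groups.

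Hypothesis B produces the 53 per group, and so most of the total of 148. If its SD and limit belong to a different scale from the one printed, the claim of 90% power holds on that other scale only. A reader cannot tell what margin in TOI-14 points the trial is sized to exclude. The gap matters more here than elsewhere because correcting the log-scale SD and limit is the purpose of this document.

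**Working it through.** **Inputs, all from the SAP's Sample size section unless noted.** Surgical mean 1.6, WW mean 3.0, SD 1.0 (A). Change score mean 3.1, SD 0.7, limit 0.4 (B). Power 0.90 and alpha 0.05, sidedness not stated. Limit of 10 points (section on the correction). Assumption: 1.6 and 3.0 are 6-month means and apply to the patients in B.

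**1. The plan's own figure.** n per group = 2 × SD² × (z₀.₉₅ + z₀.₉₀)² / limit² = 2 × 0.49 × 2.9264² / 0.16 = 52.45, so 53. This reproduces at one-sided 0.05; one-sided 0.025 would give 65. The mean of 3.1 does not enter the formula.

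**2. The change of 3.1 as a difference of logs.**
- Mean baseline log: 1.6 + 3.1 = 4.7, and e^4.7 − 1 = 108.9 points. Because the log is concave, the arithmetic mean baseline would be at least this.
- Rounding of the two means: e^(1.55+3.05) − 1 = 98.5, up to e^(1.65+3.15) − 1 = 120.5.
- WW under randomisation, starting from the same baseline: 4.7 − 3.0 = 1.7 log units of fall without surgery (about 109 to 19 points). The effect A credits to surgery is 3.0 − 1.6 = 1.4.
- The untreated fall exceeds the surgical effect even at the rounding limits: (1.55 + 3.05 − 3.05) − (3.05 − 1.55) = 1.55 − 1.50 = 0.05.

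**3. The limit of 0.4 against 10 points.** At log level m, write u = e^m. Ten points upward is ln((u+10)/u), ten points downward is ln(u/(u−10)), and 0.4 upward is u(e^0.4 − 1) points.

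| Log level | u | 10 points upward | 10 points downward | 0.4 upward, in points |
|---|---|---|---|---|
| 1.6 (surgical mean) | 4.95 | 1.105 | not defined | 2.4 |
| 3.0 (WW mean) | 20.09 | 0.404 | 0.689 | 9.9 |
| 3.1 (B's change score) | 22.20 | 0.372 | 0.599 | 10.9 |

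So 0.4 is close to 10 points at a level of 3.0 to 3.1 and far from it at 1.6.

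**4. An alternative reading: ln(1 + points improved).** Then 3.1 is e^3.1 − 1 = 21.2 points of improvement. With log-normal means, the improvement is e^(3.1+0.245) − 1 = 27.4 and the surgical score left is e^(1.6+0.5) − 1 = 7.2, so the baseline is about 35. WW at 6 months is e^(3.0+0.5) − 1 = 32.1. These figures are coherent. On this scale, however, being inferior means improving less, so 10 points is 0.599, not 0.372, and 0.4 is only 22.20 × (1 − e^−0.4) = 7.3 points less improvement. The formula also has no value for a patient who worsens by 1 point or more.

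**5. What n would be under different pairings** (one-sided 0.05, power 0.90, formula of step 1):
- Limit 0.4, SD 1.0: 2 × 8.564 / 0.16 = 107.05, so 108 per group.
- Limit 1.105, SD 1.0: 2 × 8.564 / 1.221 = 14.03, so 15.
- Limit 1.105, change of logs with both time-point SDs assumed 1.0 and correlation 0 (SD² = 2): 29.
- Limit 0.599, SD 0.7 (step 4, inferior direction): 24.

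**The case against.** The best defence is that the log(1+x) form was simply applied to the improvement in points. Step 4 shows that this gives a believable baseline, and 53 then needs no change. The limit can also be traced: ten points added at the WW mean of 3.0 is 0.404 on the printed scale itself. Finally, the transformation is tied to the sample size calculation, and the protocol, which is not at hand, may define the analysis and the handling of patients who worsen.

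Much of this stands. The log-of-improvement reading is the more plausible one, and it is wrong to say that 0.4 cannot be derived from 10 points. But neither derivation is printed, and neither supplies the right reference. The WW mean is not the level at which TT is compared with TE. On the improvement scale, 0.37 to 0.40 for 10 points runs in the direction of greater improvement, not less.

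A reader might infer more than the SAP supports:
- *That a change of 3.1 is impossible on the printed scale.* That needs the maximum score, which the SAP does not give. With an assumed maximum of 70, the largest mean change down to 1.6 is ln(71) − 1.6 = 2.66. With 100 it is 3.02, or ln(101) − 1.55 = 3.07 at the rounding limit, which would print as 3.1.
- *That 53 is a miscalculation.* It reproduces.
- *That the trial is too small.* This follows only if 0.4 is kept while the SD is changed. Converting 10 points at the surgical mean makes n fall.

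**Conclusion.** The point holds as a mismatch between hypothesis B's inputs and the printed scale. Read as a difference of logs, 3.1 is very implausible beside A's means, with an implied baseline of about 109 points (98.5 with rounding) and an untreated fall larger than the surgical effect. The limit of 0.4 stands for about 2.4 points at the surgical mean, against the 10 points the SAP says are fixed.

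The 53 per group is right for SD 0.7, limit 0.4 and one-sided 0.05. What is not shown is that it gives 90% power for a 10-point limit on log(1+TOI-14). The illustrations run from 15 to 108 per group, so the direction of any change in n is open.

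The conclusion rests on reading 1.6 and 3.0 as 6-month means for the same population as B, which the text suggests but does not state. That the inputs come from ln(1 + points improved) is a well-supported inference, not something the SAP says.

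**What to change.** In the Sample size section:

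- Print B's change score as a formula.
- State whether 10 points or 0.4 decides B, and on which scale.
- Show the conversion of 10 points to the log limit, with its reference level, in the inferior direction.
- Give the SD on that same scale.

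If the score is ln(1 + points improved), say that log(1+TOI-14) applies to A only. Also say how a patient who worsens is scored, since such patients matter in a non-inferiority comparison.

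If the score is the change in log(1+TOI-14), replace 3.1, 0.7 and 0.4 together, and restate n or the power of the planned 53 per group.

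The cost is wording, or one restated n or power figure. No extra patients are asked for.

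### Hypothesis B (TT versus TE) is sized on a log-scale change score with no mention of the baseline TOI-14 score as a covariate, so chance baseline differences can stay in the non-inferiority estimate

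*SAP*

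**What the plan says.** The SAP's Sample size section defines the outcome at two times: "Our principal outcome is a disease-specific QoL questionnaire TOI-14 score measured at baseline and at 6 months of follow-up". It reports that "the TOI-14 score was detected to be highly skewed to the right with excess zeroes at 6 months of follow-up", and continues: "so we used a natural logarithmic transformation", namely log(1+TOI-14).

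The two hypotheses are then sized on different quantities:

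- **A:** "both surgically treated groups (TE+TT combined) are superior (mean 1.6 vs 3.0, SD=1.0) compared to the follow-up (WW". These look like 6-month levels on the log scale.
- **B:** "B) TT is noninferior to TE (change score mean 3.1, SD=0.7 with non-inferiority limit=0.4". This is a change score.

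The section on the correction of the sample size gives the limit in points: "noninferiority limit=10 on the Tonsillectomy Outcome Inventory Scale (TOI-14". The document does not say how the change in B is put on the log scale. It gives no baseline mean, baseline SD or baseline-to-6-month correlation, and it names no analysis model.

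**The concern.** B asks whether TT leaves patients as well off as TE. The operation cannot influence the baseline score, yet a change score contains it. With a floor at 6 months this matters more than usual: on the points scale, a patient who ends at zero has a change equal to the baseline score. Two equally good results then count differently only because one patient started worse.

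Randomisation balances baseline on average, but not in the one trial that is run. If change is correlated with baseline, an imbalance between TT and TE moves the estimate towards or away from the limit for a reason unrelated to treatment. The baseline score that could remove this is already part of the principal outcome.

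**Working it through.** **1. The plan's own figure.** Inputs from the Sample size section: SD 0.7, limit 0.4, power 0.90, true difference 0, alpha 0.05 taken as one-sided.

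n per arm = 2 × (1.645 + 1.282)² × 0.7² / 0.4² = 52.5, so 53. This reproduces the plan. Power at 53 is 90%.

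**2. Effect of a baseline imbalance without the covariate.** The SE of TT-TE is 0.7 × √(2/53) = 0.136. Let r be the correlation of change with baseline; it is an assumption, because the document does not give it. A baseline imbalance of k standard errors shifts the estimate by k × r × 0.136. The conditional SE is 0.136 × √(1 − r²).

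Non-inferiority is declared when the estimate exceeds −0.4 + 1.645 × 0.136. At r = 0.5 the conditional SE is 0.118. A 1-SE imbalance shifts the estimate by 0.5 × 0.136 = 0.068, and 0.068/0.4 = 17%. If the imbalance favours TT, conditional type I error is 1 − Φ((0.224 − 0.068)/0.118) = 9.3%.

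| r | Imbalance | Shift | Share of limit | Type I error (against / favouring TT) | Power (against / favouring TT) |
|---|---|---|---|---|---|
| 0.3 | 1 SE | 0.041 | 10% | 2.1% / 7.9% | 85% / 95% |
| 0.5 | 1 SE | 0.068 | 17% | 0.7% / 9.3% | 82% / 98% |
| 0.5 | 2 SE | 0.136 | 34% | 0.1% / 22.8% | 63% / 99.6% |
| 0.7 | 1 SE | 0.095 | 24% | 0.1% / 9.3% | 80% / 99.7% |

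An imbalance of at least 1 SE in either direction arises in 2 × (1 − Φ(1)) = 32% of trials, and of at least 2 SE in 5%. Averaged over all imbalances, type I error is 5% and power 90%, because the SD of 0.7 already contains the baseline variation.

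**3. Can r be read from the document?** It depends on how the change was formed.

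- *Difference of logs.* With the 6-month SD of 1.0 from A, a change SD of 0.7 and a baseline log SD s, the baseline-to-6-month correlation must be ρ = (s² + 0.51)/(2s), which is at least 0.71. The slope of change on baseline is 1 − ρ/s: −0.52 at s = 0.5, about 0 at s = 0.71, +0.25 at s = 1.0 and +0.32 at s = 1.2. Even the sign is open. This reading also puts the mean log baseline at 1.6 + 3.1 = 4.7, or exp(4.7) − 1 ≈ 109 points. That looks implausible beside exp(3.0) − 1 ≈ 19 points in the WW group.
- *Log of one plus the point change.* Here 3.1 is exp(3.1) − 1 ≈ 21 points of change, with exp(1.6) − 1 ≈ 4 points left at 6 months. Adding the 10-point limit gives ln(e^3.1 + 10) − 3.1 = 0.37, close to the printed 0.4. Two simulated settings come near the printed mean and SD: baseline mean 30 with SD 10, and mean 35 with SD 12. Both use correlation 0.4 and set negative changes to zero. They give a mean of 3.0 to 3.2, an SD of 0.68 to 0.72, and r of 0.45 to 0.52. The baselines and the correlation are assumptions.

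The second reading fits the printed figures better, but the document does not confirm it.

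**4. Adding the covariate to the planned comparison.** The residual SD is 0.7 × √(1 − r²), which cannot exceed 0.7 apart from one lost degree of freedom. Patients per arm at limit 0.4 = 52.5 × (1 − r²), rounded up: 53 (r = 0), 48 (r = 0.3), 40 (r = 0.5), 27 (r = 0.7). The planned 53 suffices throughout.

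**The case against.** The strongest reply is that this is a sample size paragraph. Sizing on a change-score SD does not rule out a baseline-adjusted analysis, and the protocol, which is not shown, may specify one. That stands: a reader might infer that the plan fixes an unadjusted test, but the document is only silent. What it does fix is the change score as the quantity for B, and the remedy is compatible with any analysis already intended.

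Other stronger readings are also unsupported:

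- **That the change is untransformed.** The limit and SD for B are log-scale figures.
- **That the change mostly reflects where each arm started.** On a difference of logs the slope may be negative, zero or positive. On the log of a point change, r near 0.5 rests on assumed baselines.
- **That the error rate or the sample size is wrong.** A change-score comparison is valid under randomisation, and 53 reproduces.
- **That B could simply move to the 6-month log score with 53 per arm.** With SD 1.0, correlation 0 to 0.4 and limit 0.4, that needs about 2 × 2.927² × 1.0² × (1 − ρ²)/0.4² = 107 down to 90 per arm, and 53 gives 66% to 73% power. The limit would also change meaning: at about 4 points, 10 points more is ln((e^1.6 + 10)/e^1.6) ≈ 1.1 on the log scale. Only if the change is a difference of logs, with the baseline also logged, do the adjusted change and the adjusted 6-month score give the same contrast; the printed SDs then force the correlation to at least 0.71.

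**Conclusion.** The point holds as a design improvement, not as an error in the calculation. B is planned on a change score for an outcome with a stated floor at 6 months, and the baseline score is not mentioned as a covariate. Without it, a 1-SE chance imbalance moves the TT-TE estimate by 10% to 24% of the limit for r between 0.3 and 0.7, and by 17% at r = 0.5. The variance of the contrast is also larger than necessary: adjustment at r = 0.5 lowers it by 25%. If r is close to zero, little is gained and nothing is lost. The size of r is an assumption throughout, and its sign depends on how the change was formed, which the document leaves open.

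**What to change.** For B:

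- State how the change is formed on the log scale. If it is the log of one plus the point change, say what is done for a patient whose score worsens by a point or more, since that logarithm does not exist.
- Keep that scale, the 0.4 limit and 53 per arm.
- Take the TT-TE confidence limit from a model with baseline TOI-14 as a covariate, and state the scale on which baseline enters.

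Adjust A for baseline in the same way. Do not move B to the 6-month log score under the 0.4 limit without re-deriving both the limit and the sample size.

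The cost is SAP wording, one extra model term, and a rule for any missing baseline score. No additional patients, visits or measurements are needed.

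### Does the single alpha of 0.05 for both sample size calculations hide two different error rates?

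*SAP*

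**What the plan says.** The SAP is a short correction of the sample size. Its opening section, *Correction of sample size calculation*, lists the pre-set error rates as "alfa error=0.05, beta error=0.1" and says of the key parameters: "In this correction we do not change these parameters".

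The *Sample size* section then works on the log(1+TOI-14) scale.

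- **A, superiority.** The combined surgical groups "are superior (mean 1.6 vs 3.0, SD=1.0) compared to the follow-up (WW"). The result is "A) 7 and 28 patients in the WW and the combined TE+TT groups".
- **B, non-inferiority.** The inputs are "B) TT is noninferior to TE (change score mean 3.1, SD=0.7 with non-inferiority limit=0.4). In both calculations", after which the shared alpha and power follow. The result is "B) 53 patients in the TE and the TT groups will be needed".

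Neither section says whether 0.05 is one-sided or two-sided, and neither gives a confidence interval level for judging B. B sets the trial size: 53 per surgical group, 27 in WW by the 1:2:2 ratio, and 148 in all after allowing for 10% drop-out.

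**The concern.** A reader who checks the two results finds that no single reading of alpha gives both from the printed inputs. Two-sided 0.05 reproduces A but gives 65 per group for B. One-sided 0.05 reproduces B but gives 6 and 24 for A. One sentence about alpha therefore seems to cover two error rates.

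This would matter for B. If the analyst carried over the convention that fits A and judged non-inferiority by a two-sided 95% confidence interval, 53 per group would fall short of the stated 90% power. There is also a band of results in which the conclusion depends on the level: an observed TT disadvantage of about 0.133 to 0.176 log units passes by a 90% interval and fails by a 95% interval. If the level were chosen only after the data were seen, that choice could decide the conclusion.

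**Working it through.** **Inputs** (SAP, *Sample size*)

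- A: means 1.6 and 3.0, so a difference of 1.4; SD 1.0; allocation 1:4 (WW to TE+TT).
- B: SD 0.7; limit 0.4; allocation 1:1. The true TT-TE difference is not stated and is taken as 0.
- Both: alpha 0.05, power 0.90. Normal quantiles: 1.282 for the power; 1.645 for one-sided 0.05; 1.960 for two-sided 0.05 or one-sided 0.025.

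**Reproducing the printed sizes**

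A, WW group: n = (1 + 1/4) × (z_alpha + 1.282)² × SD² / difference².

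- Two-sided 0.05: 1.25 × (1.960 + 1.282)² × 1.0² / 1.4² = 6.70, so 7 and 28, as printed.
- One-sided 0.05: 1.25 × (1.645 + 1.282)² × 1.0² / 1.4² = 5.46, so 6 and 24.

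B, per group: n = 2 × (z_alpha + 1.282)² × (SD / limit)².

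- One-sided 0.05: 2 × (1.645 + 1.282)² × (0.7 / 0.4)² = 52.45, so 53, as printed.
- One-sided 0.025: 2 × (1.960 + 1.282)² × (0.7 / 0.4)² = 64.36, so 65.

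Drop-out: 53 / 0.9 = 58.9, so 59; 27 / 0.9 = 30; 59 + 59 + 30 = 148, as printed.

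**Power of B**

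Power = Φ(0.4 / (0.7 × √(2/n)) − z_alpha). The ratio is 2.942 at n = 53 and 3.104 at n = 59.

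| Evaluable per group | One-sided 0.05 | One-sided 0.025 |
|---|---|---|
| 53 | 90.3% | 83.7% |
| 59 | 92.8% | 87.4% |

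The noncentral t at 53 gives 89.9% and 83.0%.

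**Where the level decides the conclusion** (53 per group, SD 0.7)

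The standard error is 0.7 × √(2/53) = 0.136. The largest observed TT disadvantage that still passes is 0.4 − 1.645 × 0.136 = 0.176 by the 90% interval and 0.4 − 1.960 × 0.136 = 0.133 by the 95% interval.

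**Can the printed sizes prove two conventions?**

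The inputs are printed to one decimal, so an SD shown as 0.7 lies between 0.65 and 0.75 and a limit shown as 0.4 between 0.35 and 0.45. If only one input is varied, B at one-sided 0.025 reaches 53 with a limit of about 0.441, or with an SD of 0.635, which would not print as 0.7. If both vary together it is easier:

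- SD 0.66, limit 0.416: 2 × (3.242 × 0.66 / 0.416)² = 52.90, so 53.
- SD 0.67, limit 0.422: 52.97, so 53.
- SD 0.68, limit 0.43: 52.55, so 53.

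A is loose in the other direction. At one-sided 0.05, a difference of 1.33 with SD 1.0 gives 1.25 × (2.927 / 1.33)² = 6.05, so 7; SD 1.05 with difference 1.4 gives 6.02, so 7.

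The printed sizes therefore fit mixed sidedness exactly, but they do not exclude one convention applied to unrounded inputs.

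**The case for a change.** The strongest case for a change is that this document exists to put the sample size calculation right and names alpha among the parameters fixed beforehand, so it should say which alpha it means. B drives recruitment, both its power and its decision limit depend on the answer, and one sentence would settle it at no cost in patients. The rounding argument does not fully dispose of this: if B was in fact sized at one-sided 0.025 on unrounded inputs, the document does not say that either.

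It stands that sidedness is unstated and that stating it would be good reporting. It does not stand that the text is wrong. Non-inferiority is a directional question, and a one-sided 0.05 test of it beside a two-sided 0.05 superiority test is a common pairing; alpha of 0.05 is then true of each test as run. The claim of two error rates is an inference from rounded figures. The loss of power needs a further step, a 95% interval for B, that this document does not take. The interval level for the analysis is also something a protocol commonly fixes, and the protocol is not shown.

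**Conclusion.** No change to the plan follows. The arithmetic behind the concern is right at the printed inputs, but it uncovers a convention left unwritten, not an error or a contradiction. On the reading that the number 53 points to (one-sided 0.05, limit 0.4, SD 0.7, true difference 0), B has its stated power: 90.3% with 53 evaluable per group and 92.8% with 59. A is not in question at all: with 27 against 106 its power exceeds 99.9% even two-sided.

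The figures of about 84% (53 evaluable) to 87% (59 evaluable) apply only if B was sized at one-sided 0.05 on exactly those inputs and is then judged by a two-sided 95% interval. Nothing in this document says that it will be. An analyst who judges B at the level it was sized for meets no difficulty.

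### Does the plan need a testing order between surgery versus follow-up (A) and TT versus TE (B)?

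*SAP*

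**What the plan says.** The SAP is a correction of the sample size calculation. The corrected paragraph, under the heading Sample size, names two hypotheses on the principal outcome, on the log(1 + TOI-14) scale:

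- "A) both surgically treated groups (TE+TT combined) are superior (mean 1.6 vs 3.0, SD=1.0) compared to the follow-up (WW")
- "B) TT is noninferior to TE (change score mean 3.1, SD=0.7 with non-inferiority limit=0.4")

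Error rates are given once for both: "In both calculations $\alpha=0.05$ and $\beta=0.10$ (power=0.90"). The resulting requirements are "A) 7 and 28 patients in the WW and the combined TE+TT groups, respectively, and (B) 53 patients in the TE and the TT groups", and for the 1:2:2 allocation "we decided to recruit 27 patients into the WW group and 53 in both the TE and the TT groups". The last sentence is "Sample size estimation was performed only for the principal outcome, and other comparisons are hypothesis generating only".

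Nothing says that A is tested before B, that B depends on A, that both must succeed, or that alpha is shared. Nothing promises an overall error rate across the two hypotheses either.

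**The concern.** A non-inferiority result shows that one treatment is not much worse than another. It shows a preserved benefit only if the comparator works. Two operations that both do nothing would also look alike, and B would then succeed easily. This trial has a concurrent follow-up arm, and A tests whether surgery helps, so it seems natural to make B conditional on A. The paragraph does not.

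Two consequences would be at stake. TT could be presented as an acceptable alternative to an operation that had shown no benefit in this trial. And with 0.05 spent in full on each of two hypotheses, the chance of at least one false claim could exceed 5%.

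**Working it through.** **Inputs, all from the Sample size paragraph.** A: means 1.6 and 3.0, so a difference of 1.4, with SD 1.0. B: margin 0.4, SD 0.7. Alpha 0.05 and power 0.90 for each. Evaluable patients: 27 WW, 53 TE, 53 TT, so 27 versus 106 for A.

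**Assumptions.** The true TT–TE difference is taken as 0 for B. Sidedness is not stated and is inferred from the patient numbers. The A and B contrasts are treated as independent, because the sum and the difference of two arms of equal size and variance are uncorrelated.

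**The plan's own figures.**

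- A, two-sided 0.05, ratio 1:4: n(WW) = (1.960 + 1.282)² × 1.0² × (1 + 1/4) / 1.4² = 6.70, rounded up to 7, hence 28 surgical patients. One-sided 0.05 would give 6.
- B, one-sided 0.05: n per arm = 2 × 0.7² × (1.645 + 1.282)² / 0.4² = 52.45, rounded up to 53. One-sided 0.025 would give 65.
- Drop-out of 10%: 53/0.9 gives 59 and 27/0.9 gives 30; 59 + 59 + 30 = 148.

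All stated numbers reproduce. None depends on an order between A and B.

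**How often B would succeed while A is not significant in favour of surgery.** The t-based power of B at 53 per arm is 0.899. The standard error for A is 1.0 × √(1/27 + 1/106) = 0.216. The third column is (1 − power of A) × 0.899. The fourth is power of A × 0.899, the chance of claiming B if it were conditional on A.

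| True surgery effect (log units) | Power of A | B without A | B claimed if conditional on A |
|---|---|---|---|
| 0 | 0.025 | 0.877 | 0.022 |
| 0.3 | 0.281 | 0.646 | 0.253 |
| 0.5 | 0.634 | 0.329 | 0.570 |
| 0.7 (half the plan) | 0.897 | 0.093 | 0.806 |
| 1.0 | 0.996 | 0.004 | 0.896 |
| 1.4 (plan) | 0.999996 | 0.000003 | 0.899 |

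The high figures belong to effects far below the planned one. In every row TT and TE are truly alike, so claiming B is correct as a statement about the two operations. The third column therefore does not count false claims.

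**False claims.** B's own type I error is 5% whether or not A is tested first. The rate for at least one false claim exceeds 5% only if both null hypotheses hold together: pooled surgery equals follow-up, and TT is worse than TE by the full 0.4. With A at two-sided 0.05, and counting only claims for surgery or for TT, it is 1 − 0.975 × 0.95 = 0.074. It is 1 − 0.95² = 0.0975 if a result in favour of follow-up is counted too, although A as written claims only that surgery is superior. With equal surgical arms, this configuration needs TE to be 0.2 better than follow-up and TT 0.2 worse. At the planning values only B can err, at 5%.

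**What conditioning would achieve.** A pools TE and TT. A significant A shows that the average of the two operations beats follow-up, not that TE, the comparator in B, does.

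**The case for a change.** The strongest argument for an order is that it is nearly free where the plan expects to be. At 1.4 log units B's power stays at 0.90, N stays at 148, and one sentence would settle the point. If surgery helped much less than assumed, that sentence would stop a non-inferiority claim from resting on an unproven comparator. The last sentence of the paragraph also leaves A and B as the only comparisons not labelled hypothesis generating, so one might expect the same paragraph to relate them.

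It stands that no order is written here, that non-inferiority needs evidence that surgery works, and that many statisticians would choose a fixed sequence. It does not follow that the plan is wrong without one. A and B answer different questions: whether to operate, and which operation to use. Reasonable statisticians differ on whether such questions must form one family. The trial also supplies the evidence a reader needs, because A is itself a stated hypothesis on the principal outcome and its failure would be visible beside B. The feared harm is a guess about how B would be reported. Conditioning also costs power in the range where it matters, and it secures the comparator only in part.

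**Conclusion.** The concern does not hold. The document is a one-paragraph sample size correction; on this point it contradicts nothing and gives no wrong figure. An order between hypotheses is something a protocol may set, and the protocol was not available for this check. Followed as written, each hypothesis is tested at the level for which it was sized, and B's conclusion about TT and TE is valid at that level.

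The practical effect is negligible at the planned surgery effect (0.000003) and modest at half of it (0.093). It becomes large only if surgery does little or nothing, and then A would almost certainly show no benefit as well. Choosing an order would be a matter of preference, with a loss in B from 0.90 to 0.81 at half the planned effect.

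These figures rest on the stated SDs, a true TT–TE difference of 0, A read as two-sided and B as one-sided at 0.05, and independence of the two contrasts. The one-sided 5% level implied for B is a separate matter and is not judged here.
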